25. LOCAL NUMBER OF SUBJECTS

Considering the volume of procedures in 2019 of 48 procedures is maintained over time, it is estimated that we will be able to enroll 60 patients within 2.5 years. This sample size would allow detection of 80% reduction in POUR with a power of 80%. This number of subjects considers a refusal rate of 25% and exclusion rate of 33%.

26. CONFIDENTIALITY

The data will be stored electronically at UMass Memorial Healthcare share drive. The patients' names will be coded and paired with the corresponding MRN. All of the staff involved are HIPPA trained and are part of the UMass Memorial Healthcare/UMass Medical School.

27. PROVISIONS TO PROTECT THE PRIVACY INTERESTS OF SUBJECTS

Screening for eligibility and discussion of the research will take place when the patients visit the clinic. Patients who enroll prospectively will be asked to provide signed Authorization. For subjects who serve as historical controls, HIPAA waiver of authorizations will be used.

Data will be abstracted by the thoracic surgery data manager in a secure server and stored on the thoracic surgery shared drive password-protected hard drive provided by UMass Memorial Health Care. Any hard copies of data will be stored in a locked office in Thoracic Surgery. The system is hosted locally by UMass Memorial Health Care and employs user authentication and role-based security. Web-based data entry is via an SSL cryptographic transport protocol. Additional

INVESTIGATOR STUDY PLAN

security procedures are in place for data access. The environment logs are audited by Information Services (IS). Any additional data collection needed will be performed in RedCap and stored in the thoracic protected drive.

The PI and research team will take all the recommended steps to protect all personal information. After the matching and database creation, the individuals will be assigned a unique code in order to de-identify the data. Only the PI and the data manager analyst assigned for the project and will have access to the code list, which contains the information necessary to re-identify the data. All data are kept confidential and accessible only to researchers on this study. The paper documents will be secured and shredded after six years of the end of the study. The electronic de-identified database will NOT be destroyed and will be maintained in a secure host at the secure drive. The coded list will be destroyed using secure deletion utility after six years after the end of the study.

28. COMPENSATION FOR RESEARCH-RELATED INJURY

NA

29. ECONOMIC BURDEN TO SUBJECTS

There will be no costs associated with the use of Tamsulosin under this study. The study will cover the costs of the medication given to subjects. The ultrasound used for post void residual measurement will be provided by the Thoracic Surgery Division. For all patients who agree to participate in the prospective trial, measurements will be done by a research assistant at no cost to the patient. This study was approved for a quality improvement grant under the UMass Memorial Health Care.

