4. OBJECTIVES*

Post-Operative Urinary Retention (POUR) in Thoracic Surgery is a prospective interventional study aiming to test the hypothesis that the prophylactic use of tamsulosin prior to thoracic surgery in high-risk patients leads to reduced rates of POUR. Urinary retention is defined as eight hours without void after Foley catheter removal and symptoms or bladder volume greater than 600cc.

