5. BACKGROUND*

Post-operative urinary retention (POUR) is one of the most common post-operative complications encountered by most surgical specialties. The incidence of POUR can vary from five to 70%.¹ POUR associated factors reported in the literature include type of anesthesia, type and duration of surgery, underlying comorbidities, as well as medicines used in perioperative period. The development of POUR can increase the length of hospitalization and lead to significant morbidities such urinary tract infection, detrusor muscle dysfunction, delirium, cardiac arrhythmias among others.¹

INVESTIGATOR STUDY PLAN

POUR definition in the literature is not homogeneous, and include >200mL by bladder scanner 4 hours post-op, >500mL by bladder scanner 8 hours post-catheter removal, and >600mL by bladder scanner 4 hours after removal of indwelling urinary catheter.²⁻⁴ Urinary retention is defined in the current study as eight hours without void after Foley catheter removal and symptoms or bladder volume greater than 600 cc.

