11. PROCEDURES INVOLVED*

There will be no randomization process as this is a single arm trial. The patients will first provide consent to the research when they visit the clinic or in an inpatient setting. As part of the screening process, a physician (or physician's assistant or nurse practitioner) will review the patient's medication list for potential drug-drug interactions with tamsulosin, make a clinical decision regarding the safety of study participation, and document that this screening has occurred.

INVESTIGATOR STUDY PLAN

Since visits are being done remotely, study medication will be mailed to the subject's home and a study staff member will call to answer any questions they may have on how to take the medication. Otherwise, the medications will be dispensed in person by IDS to a research coordinator. The research coordinator will then give the medication to the patient at the time of their Pre-surgical evaluation at the Memorial campus anesthesia clinic.

Starting 2 days before surgery, patients will receive 0.4 mg Tamsulosin nightly, then on the day of surgery, 0.4 mg in holding area, and any additional consecutive days if they experience retention, which is the standard of care for all patients that present with POUR. The minimum number of days a subject could be on the study drug is 3. Tamsulosin is FDA approved and is predominantly used to treat the signs and symptoms of benign prostatic hyperplasia.

The data collection includes identification of patient and operation characteristics that correlate with development of POUR. Some of the factors we propose to study include age, operating time, type of surgery, indication for surgery, presence of epidural, development of other postoperative complications. Patients' names will be de-identified with a unique identifier and will be paired with the corresponding MRN. Principal Investigator and research coordinator will have access to those identifiers.

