13. DATA ANALYSIS AND MANAGEMENT *

Hypothesis: Prophylactic tamsulosin decreases the rate of postoperative urinary retention (POUR) rates in patients undergoing thoracic surgery

- Primary aim: compare the rates of POUR in thoracic surgery patients treated with preop tamsulosin with historic controls.

INVESTIGATOR STUDY PLAN

The rates of POUR for major procedures in UMass Thoracic service in the target population (male over 60 years old) varied from 8.3% to 33.3% over the last 5 years. In the overall thoracic population, this number was in average 8.4% and it varied from 4.3% to 9.3%.

When analyzing all major procedures performed in the 2019, 48 were performed in males over 60 years old, the study target population. The POUR rate was 33.3%. After applying the exclusion criteria on those 48 individuals, we found an exclusion rate of 33.3% where 16 individuals were excluded, 8 for using Flomax prior to surgery and 8 for using one of the following medications: Bupropion Fluconazole, TMP-SMX, Silodosin, Paroxetine Terazosin, Levofloxacin, Prazosin, Fluoxetine, Sildenafil.

The overall POUR rate was 33% and among the 32 eligible individuals, POUR rate was 28%.

Power Calculation

The incidence rate of 28% was used to estimate the possible scenarios of sample and power of analysis presented in **Error! Reference source not found.**

The number needed to treat is 60 assuming an 80% reduction of POUR with a power of 80%. Assuming the same volume of operations and taking into account the number excluded due to exclusion criteria (33%), and refusal rate of 25%, we expect to accrue 24 patients per year and achieve the number needed to treat (n=60) in 2.5 years.

All patients who fulfill the eligibility criteria and thus may benefit from the intervention (use of Tamsulosin pre-operatively) will be invited to participate in the study. **(Error! Reference source not found.)**

Table 1. Sample calculation and power-analysis in three hypothetical scenarios of varying effects of tamsulosin

	Hypothetical POUR Incidence in Intervention Group (%)	N*	Post-hoc Power estimate (I)
Tamsulosin intervention Group effect 1 (reduction of 50%)	14	150	49.3%
Tamsulosin intervention Group effect 2 (reduction of 80%)	5.6	60	80.4%
Tamsulosin intervention Group effect 3 (reduction of 90%)	2.8	32	80.4%

*N of male over 60 years old that undergo to in-patient procedures (I) <https://clincalc.com/stats/SampleSize.aspx>

INVESTIGATOR STUDY PLAN

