(II) <https://jongguri.shinyapps.io/samplepower/>

The study selected parameters are:

- Incidence, group historical control 2019 – 28%
- Incidence (expected), intervention with Tamsulosin – 5.6% (reduction of 80% in incidence)
- Subjects, group control – 32 individuals
- Subjects, group intervention (expected) -60 individuals
- Alpha - 0.05

It is expected that the population undergoing thoracic services are similar over time and it will be appropriate to use historical controls to compare with the intervention group.

Our analytical plan is to test the proportion of POUR within the study population comparing with the historical controls. The data quality will be monitored by monthly verification of the completeness of the data, missing values and accurateness of the variables collected.

If a statistically significant reduction in POUR rates is observed before the end of the study, the study will stop and Tamsulosin will be adopted as prophylaxis for this high-risk population in thoracic surgery division. If the benefit is not observed with the estimated sample, the study will be reassessed.

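### The only planned comparison does not fix how POUR is counted in either group: the 2019 control criterion is unstated, the role of the study ultrasound is undefined, and the definition has two readings

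*Combined protocol and SAP*

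**What the plan says.** Section 13 plans a single comparison: "Our analytical plan is to test the proportion of POUR within the study population comparing with the historical controls". The controls are 32 men treated in 2019, of whom it says "among the 32 eligible individuals, POUR rate was 28" per cent. The ground given for using them is "It is expected that the population undergoing thoracic services are similar over time".

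Section 4 gives the endpoint: "Urinary retention is defined as eight hours without void after Foley catheter removal and symptoms or bladder volume greater than 600cc". Section 5 repeats it for the current study, after noting that "POUR definition in the literature is not homogeneous" and listing published thresholds of 200, 500 and 600 mL. Section 10 only refers back to Section 4.

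Bladder measurement appears only in Section 29, on economic burden: "The ultrasound used for post void residual measurement will be provided by the Thoracic Surgery Division", and "For all patients who agree to participate in the prospective trial, measurements will be done by a research assistant". Section 11 (procedures) describes no bladder measurement. Its data list opens with "Some of the factors we propose to study include age, operating time, type of surgery, indication for surgery, presence of epidural" and gives no scan timing, assessor or volume.

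On the controls, Section 5 mentions a review of 2019 patients, and Section 27 mentions a HIPAA waiver and abstraction by the data manager. Neither states a POUR criterion. Section 5 puts the 2019 rate in men above 60 with major resections as high as 21%. Section 13 puts it at 33.3% in 48 men over 60 with major procedures, and at 28% after exclusions.

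**The concern.** Comparison with historical controls requires the outcome to be counted the same way in both groups. The plan argues that the populations are alike and says nothing about whether the measurement is. One group has a study-provided ultrasound operated by study staff. In the other, the method of detection is unknown.

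A difference in detection cannot be separated from a drug effect in this design. More detection in treated patients would hide a benefit. Less detection in them for any reason, or a looser count in 2019, would favour tamsulosin. The result has consequences under Section 13: a significant reduction ends the study and leads to adoption of prophylaxis in the division, while no observed benefit leads to reassessment.

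**Working it through.** **1. The two readings of the definition.**
- Reading A: (8 h without void and symptoms) or volume >600 cc.
- Reading B: 8 h without void and (symptoms or volume >600 cc).

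A man who voids within 8 h and then has more than 600 cc on a scan is an event under A and not under B. A post-void residual, the quantity named in Section 29, is the measurement on which the readings diverge.

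**2. The 2019 rates.** On 48 men, 33.3% is 16 events; 21% of the same 48 would be about 10 (0.21 × 48 = 10.1). The documents do not explain the difference. It could come from the counting rule or from the denominator.

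**3. The plan's power figure.** Inputs from Section 13: 28% in 32 controls, 5.6% in 60 treated, alpha 0.05 (taken as two-sided), stated power 80.4%. Pooled z-test:
- pooled rate = (32 × 0.28 + 60 × 0.056)/92 = 0.1339
- null SE = √[0.1339 × 0.8661 × (1/32 + 1/60)] = 0.0745
- alternative SE = √[0.28 × 0.72/32 + 0.056 × 0.944/60] = 0.0847
- power = Φ[(0.224 − 1.96 × 0.0745)/0.0847] = Φ(0.92) = 82.1%

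Exact Fisher power is 80.5%. The plan's figure reproduces, so its arithmetic is not at issue. It assumes equal detection in both groups.

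**4. More detection in treated patients.** The controls are already observed: 0.28 × 32 = 8.96, so 9/32. Against 9/32, the most treated events that still give p < 0.05 is 6 of 60 by Fisher and 7 of 60 by uncorrected chi-square (the plan names no test). Conditional power is therefore P(X ≤ 6) or P(X ≤ 7) for X ~ Binomial(60, p). The last two columns sum over all 33 × 61 possible tables instead, treating the control count as random too.

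| Detected treated rate | Fisher, 9/32 fixed | Chi-square, 9/32 fixed | Fisher, both random | Chi-square, both random |
|---|---|---|---|---|
| 5.6% (plan) | 95% | 98% | 80% | 85% |
| 7.6% (+2 points) | 83% | 92% | 68% | 74% |
| 10.6% (+5 points) | 55% | 70% | 50% | 57% |

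The 2- and 5-point shifts are assumptions; the documents give no value.

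**5. Less detection in treated patients.** Assume no drug effect and treated detection at 70% of the 2019 level, so 0.7 × 28% = 19.6% detected. With both groups random, the chance of a significant result favouring tamsulosin rises from 2.1% to 12.9% (Fisher) or from 2.6% to 15.7% (chi-square). With controls fixed at 9/32 and an underlying rate of 28%, P(X ≤ 6) rises from 0.06% to 3.6%, and P(X ≤ 7) from 0.2% to 7.7%.

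**6. Sensitivity to reclassification.**

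| Controls vs treated | Fisher p | Chi-square p |
|---|---|---|
| 9/32 vs 6/60 | 0.037 | 0.025 |
| 8/32 vs 6/60 | 0.071 | 0.056 |
| 9/32 vs 7/60 | 0.080 | 0.047 |
| 7/32 vs 3/60 | 0.029 | 0.013 |
| 6/32 vs 3/60 | 0.060 | 0.035 |

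The planned effect implies about 3 treated events (0.056 × 60 = 3.4). That result survives removal of two control events by either test; with three removed the tests disagree. Up to 4/60 also survives removal of two (7/32 vs 4/60: 0.045 and 0.032), and the chance of at most 4/60 at a true 5.6% is 76%.

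**The case against.** One definition for both groups is the natural reading. Section 10 points to a single endpoint, the primary aim in Section 13 uses one term for both groups, Section 27 calls the controls subjects and assigns abstraction to a data manager, and Section 13 promises monthly checks of completeness and accuracy. This makes a common rule likely to have been intended. It does not state one, and accuracy checks cannot supply a missing criterion.

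The size can also be overdrawn. Because the control count is known, the power with 9/32 fixed is the relevant figure, and a 2-point shift leaves it above the planned 80%. The outcomes at which one patient decides the result are uncommon at the planned effect: at a true 5.6%, 6/60 has a chance of about 7% and 7/60 about 3%. Both points stand.

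A reader might infer that study scanning will inflate the treated count and bias the trial against tamsulosin. The documents do not support that. Section 29 says who measures and who pays, not that scanning exceeds usual care, and under Reading B a residual found after a void within 8 h adds no event. A reader might also infer from the 21% and 33.3% rates that the 2019 events were counted by two different rules. A different denominator would explain the gap equally well.

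**Conclusion.** The concern holds as a gap in ascertainment whose direction and size are unknown. It is not a demonstrated bias. Followed as written, the plan tests a treated count whose use of study scans is unspecified against a control count made under an unstated rule, with a definition that can classify the same scan two ways. Modest differential detection would cost little if the drug performs as planned. A shift close to the planned event rate itself (5 points on 5.6%) would take power well below 80%, and under-detection in treated patients could raise the false-positive chance several-fold. Those sizes rest on assumed shifts, on 9/32 as the control count, and on Fisher or chi-square as the unnamed test. This should be settled before the comparison is made, but it does not by itself invalidate a result near the planned effect.

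**What to change.** - Write the POUR definition with explicit brackets.
- Before the comparison, have the data manager named in Section 27 re-abstract the 32 control charts, and classify both groups under that one definition. Reconcile the 21% and 33.3% rates at the same time.
- State how bladder volume was obtained in 2019, when the research-assistant scans are done, and whether they feed the endpoint.
- Keep the comparison under the common definition as primary. Flag treated events found only by a study scan, and report the comparison without them as a sensitivity analysis only. Dropping them from one group is asymmetric if some 2019 events were also found by scan, and this should be said.

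The cost is protocol wording, one flag on the data form and modest chart work. It needs no extra patients or visits. Some 2019 charts may lack elements of the definition; the number should be reported.

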30. CONSENT PROCESS

In order to ensure that all study staff are familiar with and will follow HRP-802 Investigator Guidance, all the team members will have a discussion joint on the components of the form. During this time, any questions or confusion will be addressed. The consent process and discussion of the research will occur during the clinic visit prior to the surgery. There will be no waiting period between recruitment and obtaining consent, since both will occur at the same time during the clinic

INVESTIGATOR STUDY PLAN

visit. In order to ensure ongoing consent, we will ask the patients again during the last visit prior to their surgery if they would still like to participate in the research.

To obtain informed consent from non-English speaking subjects, the informed consent will be translated in Spanish and Portuguese. If needed, any information can be clarified by using phone interpreter services.

31. PROCESS TO DOCUMENT CONSENT IN WRITING

We will be obtaining consent in writing. In order to ensure that all study staff are familiar with and will follow HRP-803 Investigator Guidance, all the team members will discuss the components of the form. During this time, any questions or confusion will be addressed. The consent will predominantly be obtained by the research assistants on the team.

During the COVID -19 pandemic, surgical discussions are being conducted virtually. It is therefore not feasible to obtain written consent from the subject in person. During their telehealth visit, potential subjects will be informed of the study and offered the option to participate. The study will be explained to them in detail and all questions will be answered. If they are interested, two consents will be sent to them either by standard mail, with a self-addressed stamped envelope to return the signed consent or electronically with the option of returning a signed copy electronically or by standard mail.

32. DRUGS OR DEVICES

Patients will take 0.4 mg tamsulosin for two evenings prior to surgery as well as the day of surgery prior to the operation. The medication will be dispensed from IDS. According to the HRP-425¹⁵, and the FDA Guidelines^{16,17}, the study drug, Tamulosin fulfills the following criteria, and thus is exempt of IND.

- Determination: The drug is lawfully marketed in the United States
- Determination: The investigation does not involve a route, dosage level, or use in a patient population or other factor that significantly increases the risks (or decreases the acceptability of the risks) associated with the use of the drug product

INVESTIGATOR STUDY PLAN

- Determination: Evidence of FDA approval and FDA-approved indications is in the protocol file

The project obtained from Food Drug Administration the [IND exemption ref PIND 148434](#)

INVESTIGATOR STUDY PLAN

REFERENCES

2. Kim KW, Lee J-I, Kim JS, Lee Y-J, Choi W-J, Jung H, et al. Risk factors for urinary retention following minor thoracic surgery. *Interactive CardioVascular and Thoracic Surgery*. 2015 Apr;20(4):486–92.
6. Chia Y-Y, Wei R-J, Chang H-C, Liu K. Optimal duration of urinary catheterization after thoracotomy in patients under postoperative patient-controlled epidural analgesia. *Acta Anaesthesiol Taiwan*. 2009 Dec;47(4):173–9.
